[name]: Neonatologist at Sunnybrook Health Sciences Center, Neonatal Research Director for the Department of Newborn and Developmental Pediatrics at Sunnybrook. Associate Professor in the departments of Pediatrics and Obstetrics and Gynecology at University of Toronto. She has contributed to the design and will contribute to the analysis. (1hr/ week)

[name]: Tier II Canada Research Chair, Associate Professor in the Department of Obstetrics and Gynecology at McMaster University, Associate Member of the Department of Clinical Epidemiology and Biostatistics. She has contributed to the design and will contribute to the analysis. Interpretation of the data, and knowledge translation (1 hr/ week).

[name]: Maternal-Fetal Medicine specialist at Mount Sinai Hospital, Associate Professor in the Department of Obstetrics and Gynecology and Institute of Health Policy, Management and Evaluation at University of Toronto. She has contributed to the design and will contribute to the analysis, interpretation of the data, and knowledge translation (and organize recruitment through Mount Sinai. (1hr/ week)

[name]: Scientist and statistician at the Sunnybrook Research Institute, Assistant Professor in the department of health policy, management and evaluation at the University of Toronto. He will contribute to the analysis.

Approach and Work Plan

Study Design: The proposed study is a multicentre open label **randomized controlled trial pilot**. It will include nulliparous (women who have never given birth) women with term pregnancies requiring cervical ripening prior to induction of labour and takes place at Sunnybrook and NorthYork General Hospitals . The intervention involves randomizing women to cervical ripening with either a Foley filled to 80cc, or prostaglandins. We will register the trial at Clinicaltrials.gov

Primary research question: What is the probability that eligible women will agree to be randomized into the trial evaluating high volume Foleys to prostaglandins for cervical ripening.

Primary outcome: The percentage of eligible women who are approached to participate in the study that are enrolled and randomized to either the use of a high volume Foley or prostaglandin for cervical ripening.

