Other outcomes: A rolling assessment of **the study process** to evaluate issues that may affect enrolment rates. These will be evaluated under the categories of technical, environmental, staff personnel, patient, and data collection issues. Other important processes outcomes include protocol compliance, ease of intervention, physician and patient satisfaction.

Inclusion criteria

- Nulliparous women 37 weeks and 0 days to 41 weeks and 6 days gestational age (term) requiring cervical ripening
- Health care provider feels it is possible to administer either method of cervical ripening.
- Bishop score of 6 or less
- Live, singleton, cephalic fetus

Exclusion Criteria

- Non-viable fetus
- Contraindication to cervical ripening, labour induction or labour
- Prior attempt at induction of labour in this pregnancy
- Spontaneous rupture of fetal membranes
- Evidence of labour or regular uterine contractions
- Lack of consent
- No one available to perform randomisation

How will participants be identified and followed?

An educational session for nurses, midwives, residents and physicians will be done at each centre. A detailed study information package will be available to give to women who meet entry criteria. Patients may choose to sign a consent form for the study in the antenatal period, or on presentation for cervical ripening.

Patients presenting for cervical ripening and meeting entry criteria will be invited to participate in the study and informed consent will be obtained by the research assistant. The research assistant will access the online randomization service at the Sunnybrook clinical trials unit, and the patient will be randomized to either prostaglandin or Foley filled to 80cc. At this time, all care and decision-making will be provided as per the woman's care provider. All approached women, whether they consent to be part of the study or not, will be invited to complete a short questionnaire regarding knowledge of the study prior to the day of induction and feelings towards research.

RAs will record in Redcap the date and time of delivery for enrolled women, as well as mode of delivery (vaginal or cesarean section) and any serious adverse events (maternal death or ICU admission, neonatal death or unplanned ICU admission)

Data Collection

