Data collection for patient information will be collected electronically through RedCap. Semi-structured interviews from physicians, nurses, and residents will be conducted by the PI or delegate and recorded on paper or via email.

Patient knowledge and satisfaction surveys will be provided by the research assistant and completed by the patients when approached about participating in the study.

How will outcome measures be captured?

The primary outcome measure of percent of women recruited will be captured by the number of women who undergo the randomized intervention divided by the number of women who are eligible. These numbers will be kept by the research assistants enrolling participants in the trial. Demographic data for recruited women will be captured by the research assistants from patient charts.

For process outcomes, semi-structured interviews will be conducted with staff, chief residents and charge nurses and will be recorded in writing. Patients will be asked to fill a short patient satisfaction survey. These process outcomes will be captured every 3 months.

[figure not shown]
Analysis:

The primary outcome is a descriptive statistic of number of women enrolled/ number of eligible women. Process outcomes that are quantitative in nature will be described using descriptive statistics. Qualitative process outcomes will be evaluated via group discussion and consensus at each steering committee meeting.

Sample Size calculation

The primary outcome is the proportion of eligible women who consent and are randomized into the pilot trial. It is estimated that 10-15 women will be approached per week over a 15 month time frame. This is based on a total population of 4000 deliveries per year at Sunnybrook and 6000 at North York General Hospital. . One half are nulliparous, and 90% are term. 25 % of these women will undergo induction of labour, meaning approximately 24 women per week. Not all inductions will take place during day time hours or during weekdays at Sunnybrook, however almost all inductions at North York General are pre-scheduled to take place in the afternoon during the workday, resulting in an approximation of 10-15 women approached per week or 630-975 women approached over a 15 month time frame. Our target proportion is 20%. For an expected consent rate of 20%, the sample of 130-195 will provide the 95% confidence interval around this estimate to have bounds ranging from 16.9% to 23.3%, and from 17.5% to 22.7% respectively

Timeline

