The start-up time includes hiring of RAs, ethics, contracts and data sharing agreements, information sessions and distribution of study information materials.

Recruitment and data collection will take place in 3 month blocks. The recruitment rate and feedback from clinicians will be assessed at a steering committee meeting every 3 months, after which strategy changes will be implemented.

The final analysis will take place in the final 3 months of the study.

Project Outcome Evaluation Metrics

Anticipated outcomes:

The primary outcome will be the percent of eligible participants approached for the trial that are enrolled in the trial and undergo randomization. **A recruitment rate of at least 20% will be considered a success.**

Outcome	Method of capture
Recruitment rate	Number of women enrolled/ number of eligible women as found by assessing demographics of women scheduled for induction as per birth unit records
Pt demographics of those enrolled and not enrolled (age, indication for induction, gestational age)	Patient chart
Recruitment trends/ days/ time of increases recruitment	RA recruitment data
Staff Physician, resident and charge nurse at times of enrollment	Hospital records, RA will assess when in triage
Rate of protocol compliance	Assessment of appropriate inclusion/ exclusion criteria from chart, feedback from RAs
Physician/ resident/ nursing satisfaction and attitudes towards recruitment	Semi-structured interviews q3 months
Patient satisfaction/ attitudes towards recruitment	Patient surveys
Environmental, technical, patient, staff issues, data collection issues that facilitate recruitment or deter from recruitment	Semi structured interviews q3 months

The study process will be evaluated every three months. The Steering committee will review the recruitment data, interviews and patient surveys, resulting in changes in the execution of the pilot for the next 3 months, with the goal of a) improving recruitment rate through strategy development and b) discovering unforeseen challenges to the success of the study. This information will ultimately be incorporated into the large scale study protocol.

Ethics:

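### The primary recruitment rate has two different denominators (eligible women approached, and eligible women), and the 20% success rule fits only the first

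*Combined protocol and SAP*

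**What the plan says.** The formal definition, under Approach and Work Plan (Primary outcome), is "The percentage of eligible women who are approached to participate in the study that are enrolled and randomized" to one of the two methods. Project Outcome Evaluation Metrics repeats it as "the percent of eligible participants approached for the trial that are enrolled in the trial and undergo randomization", and the 20% success rule follows in the next sentence.

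The operational text differs:

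- **How will outcome measures be captured?** "the number of women who undergo the randomized intervention divided by the number of women who are eligible". Both numerator and denominator change.
- **Analysis.** "The primary outcome is a descriptive statistic of number of women enrolled/ number of eligible women".
- **Outcome table, Recruitment rate row.** "Number of women enrolled/ number of eligible women as found by assessing demographics of women scheduled for induction as per birth unit records".
- **Main question and Hypothesis.** Feasibility is stated as 20% of eligible women, with no mention of approach.
- **Sample Size calculation.** The outcome is worded over eligible women, but the count carried into the precision statement is "630-975 women approached over a 15 month time frame".

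The plan does not say who counts as eligible for this purpose. The Exclusion Criteria include "Lack of consent" and "No one available to perform randomisation", which concern the recruitment process and not the woman's clinical suitability.

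**The concern.** This is the sole primary outcome and the only one with a success threshold. If the rate is computed as the outcome table directs, a threshold built for approached women is applied to a wider group. A rate over all eligible women cannot exceed the rate over those approached. A pilot that meets the main trial's need could therefore be reported as not a success. With several definitions in one document, the choice could also be made after the counts are known.

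The exclusion list does not settle the matter. Applying the no-one-available criterion brings eligible close to approached. Applying the consent criterion literally removes every woman who declines, and the rate tends to 100%.

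The capture numerator is a smaller issue. Read literally, it counts women who received the allocated method, which mixes adherence into a measure of recruitment.

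**Working it through.** **1. Which denominator gives the stated precision?** Sample Size calculation gives 16.9% to 23.3% and 17.5% to 22.7% around 20%. Exact (Clopper-Pearson) 95% limits at an observed 20% are:

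| Denominator | Meaning | Exact 95% limits |
|---|---|---|
| 630 | approached, low | 16.9% to 23.3% |
| 975 | approached, high | 17.5% to 22.7% |
| 130 | stated sample, low | 13.5% to 27.9% |
| 195 | stated sample, high | 14.6% to 26.3% |

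The first two rows reproduce the plan's figures and the last two do not. The precision is for women approached.

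**2. Which denominator gives the 20%?** Background supplies 1442 women needed, 5437 eligible per year, half approached and 3 years.

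- Yield at 20% of approached: 5437 × 0.5 × 0.20 × 3 = 1631, against 1442 needed.
- Required share of approached: 1442/(3 × 5437 × 0.5) = 17.7%.
- Required share of all eligible: 1442/(3 × 5437) = 8.84%.
- Ratio of the 20% bar to the second requirement: 20/8.84 = 2.26.

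The 20% is the approached requirement rounded up.

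**3. Effect at the plan's main-trial values.** Half approached and 20% consenting gives 0.5 × 20% = 10% of eligible. Reaching 20% of eligible would need 0.20/0.5 = 40% consent.

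**4. The pilot itself.** Sample Size calculation states about 24 inductions per week. Its own factors give 10000 × 0.5 × 0.9 × 0.25/52 = 21.6. It expects 10 to 15 women approached per week. The inductions are counted before the remaining entry criteria, so the number eligible is not given. As an illustration only, apply the 75% needing ripening from reference note 13, a national figure:

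- Eligible per week: 21.6 × 0.75 = 16.2.
- 20% of approached as a share of eligible: 0.20 × 10/16.2 = 12.3%, to 0.20 × 15/16.2 = 18.5%.
- Further loss to other criteria that would close the gap: 1 − 15/16.2 = 7.4% at 15 approached per week, and 1 − 10/16.2 = 38% at 10 per week.

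**5. Numerator.** A true 22% randomised falls to 20% if 1 − 0.20/0.22 = 9.1% of randomised women do not receive the allocated method. That rate is assumed, since the documents give none. The numerator therefore matters only close to the threshold.

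**The case against.** The strongest reply is that eligible and approached are meant to be the same women in the pilot. The section on identifying participants says that women who present for ripening and meet entry criteria will be invited, and the entry criteria exclude women when nobody can randomise them. That could remove the off-hours inductions that explain the 10 to 15 per week. The research assistants keep both counts, which suggests a log of women they met. Sample Size calculation slides from eligible to approached as if the words were interchangeable. On this reading, the capture and Analysis denominators agree with the formal definition and only the table stands apart.

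This reading is plausible and could narrow the gap, perhaps to little. It is not stated as the rule for the denominator, however, and it does not repair the table, which names a separate source not described as showing who was approached.

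Other points deserve weight:

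- The 2.3-fold figure is a main-trial figure and does not measure the pilot's gap.
- The literal consent reading is surely unintended. It shows only that the exclusion list cannot supply the denominator without an added rule.
- Study Design describes the intervention as randomising women, so the capture numerator may simply mean randomised.
- The outcome is descriptive, and counting unapproached women errs towards calling a feasible pilot unsuccessful. A pass mark is attached all the same, and the steering committee reviews the recruitment rate every 3 months.

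**Conclusion.** The concern holds, and the text should be corrected before the primary outcome is computed. The formal definition, the derivation of the 20% and the stated confidence limits all use eligible women approached. The table uses a wider source, and the capture and Analysis wording allows one.

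On the main trial's own figures, 20% of all eligible women is about 2.3 times the 8.8% needed. With half approached, one set of data gives 20% or 10% depending on the section followed. This rests on the half-approached assumption in Background.

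For the pilot, the direction of the difference is certain whenever some eligible women are not approached, but its size is unknown. The 12.3% to 18.5% range depends on an assumed 75% needing ripening and on no further exclusions. The numerator difference is secondary.

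**What to change.** Adopt one definition throughout:

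- **Numerator:** women randomised, whatever they later receive.
- **Denominator:** women approached who meet all inclusion criteria and none of the exclusions, leaving aside lack of consent and no one being available to randomise. State that these two do not remove a woman from the clinically eligible count.

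Align the main question, Hypothesis, capture, Analysis and Sample Size wording and the Recruitment rate row of the table with the existing formal definition. Keep the 20% rule for this rate only.

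Have the research assistants log each eligible woman approached. Report two further descriptive measures without the 20% rule: approached over clinically eligible, using birth-unit records, and receipt of the allocated method among those randomised. The first shows whether the main trial's half-approached assumption is realistic.

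The cost is protocol wording and one explicit log item. The assistants already keep recruitment counts and offer a questionnaire to all approached women, and birth-unit records are already a planned source. The sample size, stated precision and threshold do not change.

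### The sample-size paragraph does not reproduce from its own inputs: the weekly flow drops the term factor, 630 does not fit its companion figures, and the intervals are attached to the wrong n

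*Combined protocol and SAP*

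**What the plan says.** The Sample Size calculation section starts from 4000 deliveries a year at one site and 6000 at the other. It then applies three fractions: "One half are nulliparous, and 90% are term", and "25 % of these women will undergo induction of labour, meaning approximately 24 women per week". Because not every induction falls in hours when women can be approached, it reduces this to "10-15 women approached per week or 630-975 women approached over a 15 month time frame". With an expected consent rate of 20%, it concludes that "the sample of 130-195 will provide the 95% confidence interval around this estimate to have bounds ranging from 16.9% to 23.3"%, and gives 17.5% to 22.7% for the upper end of the range.

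The denominator of the recruitment rate is described in two ways. The Primary outcome statement uses women approached: "The percentage of eligible women who are approached to participate in the study that are enrolled and randomized". The text under Anticipated outcomes agrees: "the percent of eligible participants approached for the trial that are enrolled in the trial and undergo randomization". The section on how outcome measures are captured instead has the count "divided by the number of women who are eligible", and the Analysis section says "The primary outcome is a descriptive statistic of number of women enrolled/ number of eligible women". The outcome table under Anticipated outcomes also uses eligible women, identified from birth unit records.

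**The concern.** These are the pilot's only sample-size and precision figures, and they cannot all be obtained from the inputs printed beside them. There are three slips:

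1. The weekly flow appears to omit one of the listed factors.
2. The lower number approached is inconsistent with the upper number and with both ends of the range randomised.
3. The confidence intervals are credited to the number of women randomised, although the proportion being estimated has women approached (or eligible) as its denominator.

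The third matters most. A reader who takes 130-195 as the n would credit that n with intervals less than half as wide as it can give.

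**Working it through.** **Inputs**, all from the Sample Size calculation section: 4000 + 6000 = 10,000 deliveries a year; 0.50 nulliparous; 0.90 term; 0.25 induced; 10-15 approached per week for 15 months; expected proportion 0.20. I assume a 52-week year.

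**1. Weekly flow**
- Plan's figure: 10,000 × 0.50 × 0.25 / 52 = 24.04. The printed 24 appears only when the term factor is left out.
- All stated factors: 10,000 × 0.50 × 0.90 × 0.25 / 52 = 21.63, about 10% lower.

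**2. Number approached and number randomised**

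The plan does not give the number of weeks. 975 / 15 = 65, and 15 × 52 / 12 = 65.0.

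| Weeks | Approached (10-15 per week) | Randomised at 20% |
|---|---|---|
| 65 | 650-975 | 130-195 |
| 63 | 630-945 | 126-189 |
| Plan prints | 630-975 | 130-195 |

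Three of the four printed counts fit 65 weeks and only 630 fits 63. No single duration gives all four.

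**3. Confidence intervals**

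The plan names no interval method, so I tried three at a proportion of 0.20 (95%, two-sided, in %). For x randomised out of n, the exact (Clopper-Pearson) bounds are the 0.025 quantile of Beta(x, n − x + 1) and the 0.975 quantile of Beta(x + 1, n − x). Wald is 0.20 ± 1.96 × √(0.16 / n).

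| x / n | Wald | Wilson | Exact |
|---|---|---|---|
| 126 / 630 | 16.88-23.12 | 17.06-23.30 | **16.94-23.34** |
| 130 / 650 | 16.92-23.08 | 17.11-23.25 | 16.99-23.29 |
| 189 / 945 | 17.45-22.55 | 17.57-22.67 | 17.49-22.70 |
| 195 / 975 | 17.49-22.51 | 17.61-22.63 | **17.53-22.65** |
| 26 / 130 | 13.12-26.88 | 14.03-27.69 | 13.50-27.92 |
| 39 / 195 | 14.39-25.61 | 14.99-26.17 | 14.63-26.31 |

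- The printed lower-end interval, 16.9-23.3, matches the exact interval for 126/630. For 130/650 the exact interval prints as 17.0-23.3. The sentence therefore pairs a 130 that comes from 650 with an interval that comes from 630.
- The printed upper-end interval, 17.5-22.7, matches the exact interval for 195/975. It also matches 189/945, so it cannot decide between 65 and 63 weeks.
- No method gives the printed bounds with n = 130 or 195. Exact half-widths there are (27.92 − 13.50) / 2 = 7.2 and (26.31 − 14.63) / 2 = 5.8 points. For 630 and 975 they are (23.34 − 16.94) / 2 = 3.2 and (22.65 − 17.53) / 2 = 2.6 points.

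**The case against.** The best defence is that nothing of consequence changes.

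- **Weekly flow.** It feeds no later figure. The step down to 10-15 per week is a judgement about working hours, and 21.6 still exceeds 15.
- **630 or 650.** The difference moves each bound by about 0.05 point.
- **Wrong n.** The number approached and the 20% rate stand just before the sentence, so an attentive reader can see that 130-195 is the expected yield. The analysis is descriptive and success is a rate of at least 20%.

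All of this stands. It limits the weight of the point but does not make the paragraph correct.

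It can also be said that 65 weeks is inferred, and that the lower interval was evidently calculated on 630. That is fair: 65 weeks is better supported, but the sponsor should confirm it.

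Finally, eligible versus approached is a question of outcome definition rather than arithmetic, and parts of the plan narrow the gap. Women are excluded when nobody is available to randomise them. Research assistants keep the counts. The Background section ties the 20% to women approached: 5,437 × 0.5 × 0.20 × 3 years = 1,631, which covers the 1442 needed for the large trial. These support approached as the intended denominator. They do not remove the outcome table's count from birth unit records, which could include women never approached, so the corrected sentence has to say which n it uses.

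**Conclusion.** The concern holds, as a minor correction. The weekly flow should be about 22 rather than 24. The lower number approached should be 650 rather than 630 if recruitment runs 65 weeks. The stated intervals belong to the women approached, not to the 130-195 randomised. Planned precision is essentially right once the correct n is named: at the lower end the exact interval goes from 16.94%-23.34% to 16.99%-23.29%, and the upper end is unchanged. The wider intervals at n = 130 and 195 show only that the wrong n is named; they are not a loss of planned precision. No success or stopping rule changes.

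This rests on a 52-week year, on 65 weeks inferred from the plan's other counts, on the exact method inferred from the match to the printed bounds, and on eligible women approached being the denominator.

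**What to change.** In the Sample Size calculation section, change 24 per week to about 22 and, once the sponsor confirms 65 weeks, 630 to 650. Replace the last sentence with:

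> For an expected consent rate of 20%, approaching 650-975 women (expected 130-195 randomised) gives exact (Clopper-Pearson) 95% confidence intervals of 17.0%-23.3% and 17.5%-22.7% respectively.

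If 63 weeks was intended, keep 630, change the upper end to 945 and the number randomised to 126-189; the printed intervals then stand as 16.9%-23.3% and 17.5%-22.7%.

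Use eligible women approached as the denominator in the Sample Size calculation, outcome-capture and Analysis sections and in the outcome table. If all eligible women were meant instead, 650-975 is not the n either, and the n and intervals must be restated for that count.

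The cost is one rewritten paragraph and aligned wording, with no extra participants. If the outcome table was meant literally, the count would also have to come from the research assistants' record of approaches rather than from birth unit records.
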